#### **4.4.1 Assumption Checks and Alternative Analyses**

Primary outcome will be assessed for normality within the two treatment arms. Levene's test for equal variances will be performed. Standard residual diagnostics (normality, homoscedasticity) after *tobit* regression model will be performed. In the case of serious deviations, either non-parametric tests will be considered or transformation of the outcome, or both.

#### **4.4.2 Missing Data**

Patients will be excluded from analyses of primary outcome if data on the outcome variable is missing.

#### **4.4.3 Sensitivity Analyses**

None.

#### **4.4.4 Subgroup Analyses**

None planned for primary outcome.

### **4.5 Methods for Dichotomous Secondary Outcomes**

**The share of patients not reaching adequate pain relief within 48 hours (Outcome b)**

This outcome is assessed by whether physician and patient conclude that further adjustments in pain medication are required after 48 hours. Physicians may for convenience reasons during follow-up period convert from SC to IV for patients who have a long-term venous catheter. This will not be seen as an adjustment unless the intention is to improve pain treatment or infusion rate and/or bolus dose also is changed.

#### **4.5.1 Descriptive Statistics**

Categorical data will be presented by numbers and percentages.

#### **4.5.2 Primary Inferential Analysis**

Z-test for proportions will be applied to compare the secondary outcome (b) between the groups.

---

### 4.5.3 Effect Estimates

Difference in proportions will be presented together with the corresponding 95% CIs.

### 4.5.4 Assumption Checks and Alternative Analyses

Including 30 participants in each arm implies large enough groups to assume approximately normal distribution of z-statistics.

### 4.5.5 Missing Data

The patients who are considered not to have achieved pain control at the end of 48-hour double blind treatment will be excluded from PP analyses but included in ITT analyses.

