#### 3.4.2 Protocol Deviations

The following pre-defined important protocol deviations are regarded to affect the efficacy of the intervention (See also Protocol Deviation Handling Plan):

- Subjects entered into the study even though they did not meet the entry criteria.
- Subjects who developed withdrawal criteria (from treatment or study) during the study but were not withdrawn.
- Subjects who received the wrong treatment or incorrect dose.
- Subjects who received an excluded concomitant treatment.
- Failure to register time from start of continuous IMP infusion until the last dose adjustment
- Withdrawn consent
- Other serious breaches according to the clinical trial protocol

The number (and percentage) of patients with major and minor protocol deviations will be summarized by treatment group with details of type of deviation provided. The patients that are included in the intention to treat analysis data set will be used as the denominator to calculate the percentages. No formal statistical testing will be undertaken.

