### 3.5 Analysis Populations

The enrolled set will include all patients who have provided informed consent and have been included in the study database.

**The Full Analysis Set (FAS)** will be defined as all patients randomly assigned to a treatment group regardless of whether they received any study treatment after randomization.

**The Safety Analysis Set (SAS)** will include all patients that receive any study treatment after randomization.

**The Per Protocol (PP) population** will include all randomized patients who meet the study eligibility criteria, and complete the study according to protocol with no major protocol deviations affecting the treatment efficacy.

**The intention to treat (ITT) population** will include all patients who were randomly assigned to a treatment group, regardless of whether they complete the treatment as planned: Main outcomes will be analyzed based on intention to treat principle. Supplemental PP analyses will be based on patients who completed the 48-hour double blind period.

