## **4.3 Secondary Outcomes Definitions**

- b) The share of patients not reaching adequate pain relief within 48 hours.
- c) Comparison of pain score every 12 hours during the 48 hour period.
- d) Number of bolus doses the first 24- and 48 hours (assessed every 12 hours.)
- e) Time from bolus administration of morphine to clinically significant pain relief (reduction of 2 on NRS 0-10)

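### Section 4.5.5 drops from the per-protocol set the patients who are the outcome b events, so a per-protocol analysis of outcome b is 0% against 0% with no computable test

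*SAP*

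**What the plan says.** - **The outcome.** SAP section 4.3 defines outcome b as "The share of patients not reaching adequate pain relief within 48 hours". Section 4.5 says it is assessed by "whether physician and patient conclude that further adjustments in pain medication are required after 48 hours". A patient who still needs adjustment is therefore an event.
- **The analysis.** Section 4.5.2: "Z-test for proportions will be applied to compare the secondary outcome (b) between the groups". Section 4.5.3: "Difference in proportions will be presented together with the corresponding 95% CIs".
- **The exclusion.** Section 4.5.5, headed Missing Data and placed within the methods for outcome b, says that patients "considered not to have achieved pain control at the end of 48-hour double blind treatment will be excluded from PP analyses". The same sentence keeps them in the ITT analyses.
- **The PP set.** Section 3.5 describes it twice. The first description takes eligible randomized patients who "complete the study according to protocol with no major protocol deviations affecting the treatment efficacy". The second reads: "Supplemental PP analyses will be based on patients who completed the 48-hour double blind period". Neither mentions pain response.
- **Deviations.** Section 3.4.2 introduces its list with "The following pre-defined important protocol deviations are regarded to affect the efficacy of the intervention". Lack of pain control is not on the list.

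**The concern.** A PP set should be defined by eligibility, treatment received and adherence, not by the result being compared. Section 4.5.5 selects patients on the result. For outcome b it removes exactly those who would be counted, so the supplemental PP analysis cannot show a difference of any size.

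The rule also conflicts with section 3.5. A patient who completes the 48 hours without deviation but without pain control is in the PP set under 3.5 and out of it under 4.5.5. If this is settled only once data are unblinded, the choice of set depends on the data.

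Finally, the rule stands under Missing Data although these patients have an observed outcome. Section 4.5.5 is left without a rule for a value that really is missing.

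**Working it through.** **Starting point.** The SAP gives no expected rate for outcome b, so there is no figure of its own to reproduce there. The event counts below are assumptions. From the SAP come 30 patients per arm (4.5.4, 4.9) and a two-sided 5% level (2.4.2).

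**Step 1: outcome b with events kept.** This is the ITT analysis, and also PP under 3.5 if everyone completes 48 hours without a major deviation. Assume 3/30 and 9/30.
- Difference = 0.30 − 0.10 = 0.20; pooled proportion = 12/60 = 0.20.
- Pooled SE = √(0.20 × 0.80 × 2/30) = 0.1033; z = 0.20/0.1033 = 1.94; p = 0.053.
- Unpooled SE = √(0.10 × 0.90/30 + 0.30 × 0.70/30) = 0.10; Wald 95% CI = 0.20 ± 1.96 × 0.10 = 0.004 to 0.396.

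The interval just excludes zero while p is just above 0.05, because the test uses the pooled SE and the interval the unpooled one.

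**Step 2: outcome b in PP under 4.5.5.** Remove the events from numerator and denominator.

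| Assumed events (of 30 each) | z, p with events kept | PP under 4.5.5 | z in PP |
|---|---|---|---|
| 3 vs 9 | 1.94, 0.053 | 0/27 vs 0/21 | 0/0 |
| 6 vs 12 | 1.69, 0.091 | 0/24 vs 0/18 | 0/0 |
| 9 vs 15 | 1.58, 0.114 | 0/21 vs 0/15 | 0/0 |

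In each row the pooled proportion is 0, the SE is √(0 × 1 × …) = 0, and the Wald CI is 0 to 0. The result does not depend on the assumed counts.

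**Step 3: what would follow if the rule reached outcome a.** The rule stands in the outcome b section, and outcome a has its own missing-data rule without this exclusion (4.4.2). The general reference to PP analyses still leaves room to apply it there. The inputs from 4.9 are a 12 h difference and SD 12 h. The SAP's 23 per arm from these inputs reproduces: exact t-test power is 0.8997 at 22 and 0.9125 at 23.

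Assume further that times T are normal, that failure on b means a latent T above 48 h, and the arm means shown. With z = (48 − μ)/12:
- mean after exclusion = μ − 12 φ(z)/Φ(z);
- mean capped at 48 h = Φ(z) × (mean after exclusion) + 48 × (1 − Φ(z));
- share removed = 1 − Φ(z).

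For μ = 36: z = 1; mean after exclusion = 36 − 12 × 0.2420/0.8413 = 32.55 h; capped mean = 0.8413 × 32.55 + 48 × 0.1587 = 35.00 h; removed 15.9%.

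| Assumed means (h) | Capped difference, all patients | Difference after exclusion | Loss | Removed, faster/slower arm |
|---|---|---|---|---|
| 18, 30 | 29.65 − 17.98 = 11.67 | 28.33 − 17.79 = 10.55 | 1.13 | 0.6% / 6.7% |
| 24, 36 | 35.00 − 23.90 = 11.10 | 32.55 − 23.34 = 9.21 | 1.89 | 2.3% / 15.9% |
| 30, 42 | 39.63 − 29.65 = 9.98 | 35.89 − 28.33 = 7.56 | 2.42 | 6.7% / 30.9% |

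Differences and losses are taken from unrounded values. Flooring T at 0 leaves the losses unchanged. If failure on b is unrelated to T, there is no such shrinkage and only power falls.

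**The case against.** - **The two terms are never equated.** Section 4.5.5 speaks of pain control, outcome b of adequate pain relief and the need for further adjustment. If they differ, 0% would not be exact. But the rule sits inside the outcome b section, both refer to status at 48 hours, and the SAP defines no separate concept. Even if they did differ, PP membership would still depend on response and still conflict with 3.5.
- **No PP test of outcome b is expressly scheduled.** Sections 4.5.2 and 4.5.3 name no population, and 4.5.6 plans no sensitivity analyses. This is fair, but 3.5 provides for supplemental PP analyses and 4.5.5 sets a PP rule in this very section. If none is intended, the rule has no purpose there.
- **Section 4.6.6 covers missing values for outcome b.** It does name b among the outcomes for which all patients with at least one measurement are included. Its reason is the linear mixed model, which does not fit a single binary outcome compared by a z-test. It needs to be reconciled with 4.5.5, but does not fill the gap.
- **Documents not shown may add PP criteria.** Section 3.4.2 refers to a deviation handling plan and to the protocol. What stands is that, within the SAP, 4.5.5 adds a criterion absent from 3.5.
- **The outcome a figures are hypothetical.** They are: they rest on several assumptions, and a patient needing adjustment after 48 h may have had the last recorded one well before. The finding does not depend on them.
- **The damage is limited.** This stands. A 0/0 result would be seen at once and could not support a false claim.

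**Conclusion.** The concern holds and should be fixed. Reading lack of pain control at 48 hours as the outcome b event, the PP analysis of outcome b is 0% against 0% at any true rates, and neither the z-test nor a Wald interval carries information. Independently of that reading, 4.5.5 makes PP membership depend on response, which neither statement in 3.5 does.

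The defect is confined to the supplemental PP analyses. The ITT analyses keep these patients and are untouched, and the sample size is not affected. The possible loss of about 1.1 to 2.4 h in a PP comparison of outcome a is a conditional remark only. It requires the rule to be carried over to that outcome and failure to go with times above 48 h.

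**What to change.** 1. Delete the pain-control exclusion from 4.5.5.
2. State one PP definition in 3.5, based on eligibility, completion of the 48-hour period and absence of the deviations in 3.4.2 that count as major, regardless of pain response. Use it for every PP analysis. Section 3.4.2 calls its list important but then tabulates major and minor deviations, so say which listed items are major.
3. Let 4.5.5 say how a patient whose outcome b value is actually missing is handled, and bring the mention of outcome b in 4.6.6 into line with it.

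The cost is SAP wording only, with no new data. The change should be made before unblinded data are analysed, so that the PP set is not chosen with results in view.

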### 4.5.6 Sensitivity Analyses

None.

### 4.5.7 Subgroup Analyses

None.

## 4.6 Methods for Continuous Secondary Outcomes

### 4.6.1.1 *The pain score recorded every 12 hours during the 48 hours period. (Outcome c)*

Linear mixed model with random effects for patients and slopes will be estimated to assess the difference between the groups in overall trend in pain score. The model will include fixed effects for (possibly non-linear polynomial for) time, group dummy and the interaction between the two. Post hoc analyses will be performed to assess between-group differences at each time point as well as within-group changes.

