##### **Secondary**

- b. There is no difference in number of bolus doses from PCA in the SC and IV group.
- c. There is no difference in pain score as assessed by NRS for the whole 48-hour period
- d. There is no difference in time from administration of a bolus dose to decrease in pain (change of 2 on 0-10 NRS) intensity and to acceptable pain relief between the SC and IV groups.

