### **Secondary**

- b. The number of bolus doses after 24 and after 48 hours in the two groups are different
- c. The pain score in the groups differ during the 48-hour period
- d. Time from bolus dose to clinically significant pain relief (change of 2 on 0-10 NRS) differ between the SC and IV group

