### 4.6.3 Primary Inferential Analysis

Independent samples t-test for outcomes d) and f). In addition, linear mixed model for outcome c) and f).

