### 4.6.4 Effect Estimates

Mean differences between the groups at each time point with the corresponding 95% CIs.

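### Pain score (outcome c): the hypothesis concerns the whole 48 hours, but the model is aimed at a trend of open polynomial degree, and collected baseline scores have no stated use

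*SAP*

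**What the plan says.** Outcome c is described in several places in the SAP.

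- Section 2.4.1.1, null hypothesis: "There is no difference in pain score as assessed by NRS for the whole 48-hour period". Section 2.4.1.2, alternative: "The pain score in the groups differ during the 48-hour period".
- Section 4.3, definition: "Comparison of pain score every 12 hours during the 48 hour period".
- Section 4.6.1.1 fits a linear mixed model with patient-level random intercepts and slopes "to assess the difference between the groups in overall trend in pain score". Its fixed part reads: "The model will include fixed effects for (possibly non-linear polynomial for) time, group dummy and the interaction between the two". Neither a degree nor a rule for choosing one is given. The section adds: "Post hoc analyses will be performed to assess between-group differences at each time point as well as within-group changes".
- Section 4.6.3, on the primary inferential analysis: "In addition, linear mixed model for outcome c) and f". No coefficient or contrast is named.
- Section 4.6.4, effect estimates: "Mean differences between the groups at each time point with the corresponding 95% CIs".

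Section 4.1.1 collects NRS at 0, 12, 24, 36 and 48 hours and takes 1 to 2 points between arms as clinically significant. The SAP does not say whether the 0 h value is a response, a covariate or a mean shared by the arms.

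The model for c is reused for bolus counts (Section 4.6.1.2) and for saturation, sedation and respiration (Section 5). Section 5 also compares opioid side effect scores at 24 and 48 hours by t-test, while Table 1 schedules that questionnaire at baseline as well.

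**The concern.** A group-by-time term asks whether the arms' courses diverge. The stated hypothesis asks whether pain differs over the period. If 0 h is a covariate and the arms differ by the same amount at every later visit, there is no interaction at all, yet the null is false. If 0 h is the first response, such a step does produce an interaction, but a straight line fits it badly.

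The quantity tested (trend) is also not the quantity reported (time-point differences). With a polynomial above degree 1 the interaction has several terms, and no joint test is named. Left open, the degree can be settled after the data are seen.

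Separately, baseline scores that predict later scores are collected without a stated use in the comparison. With 23 to 30 patients per arm, that precision is worth having. At stake is how clearly a secondary outcome and some safety comparisons can be read, not the primary result.

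**Working it through.** **Inputs from the SAP.** Visits at 0, 12, 24, 36 and 48 h, and a relevant difference of 1 to 2 points (4.1.1); two-sided 5% without multiplicity adjustment (2.4.2); 23 per arm before and 30 after allowance for dropout (4.9). The SAP gives no power figure for c. For the primary outcome, a 12-hour difference with SD 12 and 90% power needs 22.02 per arm by the noncentral t, so the stated 23 is reproduced.

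**Assumed, not in the SAP.** NRS SD 2.2; equal correlation r = 0.3 / 0.5 / 0.7 between visits; 0 h in the response for the trend test; the effect shapes below.

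**What each test sees.** The linear slope uses weights (−2, −1, 0, 1, 2)/10 per 12 h.

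- Step (0, 1, 1, 1, 1): slope (−1 + 0 + 1 + 2)/10 = 0.20; 12–48 h mean 1.
- Gradual (0, 0.25, 0.5, 0.75, 1): slope (−0.25 + 0 + 0.75 + 2)/10 = 0.25; mean 2.5/4 = 0.625.
- Early and transient (0, 2, 1, 0, 0): slope −2/10 = −0.20; mean 3/4 = 0.75.

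**Worked case, step, r = 0.5, 23 per arm.**

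- Slope: variance 2.2² × (1 − 0.5)/10 × 2/23 = 0.0210, SE 0.145, ratio 0.20/0.145 = 1.38, power 27%.
- Baseline-adjusted 12–48 h mean: variance 2.2² × [(1 + 3r)/4 − r²] × 2/23 × (1 + 1/42) = 4.84 × 0.375 × 0.0870 × 1.024 = 0.162, SE 0.402, ratio 1/0.402 = 2.49, power 68%.

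**Power (%) at 23 per arm, r = 0.3 / 0.5 / 0.7.** Group-by-time tests use the noncentral F.

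| Shape | Linear | Degree 2 | Degree 3 | Adjusted 12–48 h mean |
|---|---|---|---|---|
| Step | 21 / 27 / 41 | 24 / 33 / 51 | 23 / 31 / 49 | 67 / 68 / 80 |
| Gradual | 30 / 39 / 59 | 22 / 30 / 47 | 19 / 25 / 40 | 32 / 33 / 41 |
| Early, transient | 21 / 27 / 41 | 49 / 64 / 87 | 75 / 89 / 99 | 44 / 45 / 55 |

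Equal correlation leaves out the random slopes that 4.6.1.1 specifies. With random slopes (intercept/slope/residual SD 1.2/0.3/1.8, 1.5/0.3/1.5 or 1.8/0.4/1.2, slope per 12 h), the adjusted mean has 57–59% power for the step and 27–28% for the gradual shape.

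**Error rate with no true difference** (40,000 simulated trials per setting, 23 per arm, same three r):

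- best of degrees 1 to 4 only: 10.4 / 10.4 / 10.6%
- any of the four post-baseline time points: 17.7 / 15.6 / 12.8%
- linear trend or any time point: 20.7 / 19.2 / 16.8%
- any degree or any time point: 23.2 / 22.3 / 20.7%

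**Precision from baseline.**

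- Side effect score at one visit: the variance cut is r² = 9 / 25 / 49%.
- Mean 12–48 h NRS, against an analysis that ignores 0 h: r² ÷ [(1 + 3r)/4] = 0.09/0.475, 0.25/0.625, 0.49/0.775 = 19 / 40 / 63%; 11–45% if correlation decays at 0.5–0.8 per 12 h.
- If 0 h is already a response in the random-slope model, a common baseline mean may cut the 48 h variance by only 1–10% (0–48 h correlation 0.20–0.25). For the 12–48 h mean the cut is 14–29% at a 0–48 h correlation of 0.25 and 54–68% at 0.61, depending on the time coding.

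**The case against.** The strongest reply is that a hierarchy can be read from the text. Section 4.6.3 makes the mixed model the main analysis of c, 4.6.1.1 gives its purpose as the trend and labels time-point contrasts post hoc, and 4.6.4 only says how effects are displayed. The one rule for claiming superiority (2.4.3) concerns the primary outcome.

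Much of this stands. A reader might infer that c could be declared positive on any single time point, with a 17 to 23% chance of a false finding. The documents do not support that: those rates are upper limits, driven mostly by contrasts the SAP itself calls post hoc. If only the degree is free, the rate is about 10%. The reply does not, however, make the trend an answer to the whole-period null, fix the degree, or reconcile the tested with the reported quantity.

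A reader might also infer that the 12–48 h mean is the required or more powerful test. Neither follows. The hypothesis does not speak of an average. The linear trend is stronger for a gradual difference at r = 0.5 and 0.7, and a degree 2 or 3 interaction is stronger for an early transient one. That last shape is plausible, since the primary question is how quickly pain control is reached.

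On baseline, the reference to within-group changes in 4.6.1.1 suggests that 0 h is already a response, in which case the gain at 48 h may be small. The side effect t-test is valid and concerns a separate, exploratory measure (Section 1.3.2, item vi). That item asks about change across 0, 24 and 48 hours, so using the baseline score fits the SAP's own question.

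**Conclusion.** The point holds as a mismatch between hypothesis, model and reported estimate for one secondary outcome, together with unused or undefined baseline scores. The case for change rests on agreement with the stated hypothesis and on precision from data already collected, not on a general power advantage.

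The best-supported gain is the 9 to 49% variance reduction for side effect scores at assumed correlations of 0.3 to 0.7. The gain for NRS depends on the correlation and on whether 0 h is already a response. Every power figure rests on an assumed SD, correlation and effect shape, and shows only that the choice of test matters. The unadjusted comparisons are valid. The primary outcome and the decision rule are not touched. This is an improvement to consider.

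**What to change.** 1. **Section 5:** compare opioid side effect scores at 24 and 48 hours by ANCOVA on the baseline score.
2. **Section 4.6.1.1, 0 h score:** state that 0 h NRS is a response with a mean common to both arms, or enter it as a covariate.
3. **Section 4.6.1.1, lead test:** name one test for c that answers the whole-period hypothesis. Options are the average group difference over 12–48 h or a joint test of the group differences at the post-baseline visits. Put the matching estimate and interval in 4.6.4, and list the trend and the remaining contrasts as supporting.
4. **Time coding:** fix it before unblinding. Treating the five scheduled visits as categories is feasible for c; state the form for bolus counts (4.6.1.2) too. It does not carry over to the 2-hourly and post-bolus safety measures in Section 5, which have about 48/2 + 1 = 25 scheduled times plus unscheduled ones. For those, fix a separate continuous-time form.

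The cost is SAP wording only: same data, visits and software. It should be done before the data are seen.

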### 4.6.1.2 *Number of bolus doses the first 24- and 48 hours (Outcome d)*

Number of bolus doses after the first 24- and 48 hours will be compared between the treatment arms by an independent samples t-test. In addition, linear mixed model with the same random and fixed effects as for outcome c will be estimated to assess a difference between the groups in overall trend in number of boluses. Post hoc analyses will be performed to assess between-group differences at each time point as well as within-group changes.

Bolus doses will be categorized and summarized as

- Total number of bolus doses.
- Bolus dose without effect (change in NRS less than 2) but without need of further titration.
- Bolus doses without effect (change in NRS less than 2) and the need for further titration (repeated bolus dose within one hour).

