### 1.3.1.2 Secondary research questions

- b) Is there a difference in number of bolus doses after 24 and 48 hours between the groups
- c) Is there a difference in pain score (NRS 0-10) between the groups
- d) Is there a clinically significant difference between SC and IV administration of morphine in time from administration of bolus dose to clinically significant pain relief?

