### 4.6.6 Missing Data

All patients with at least one measurement will be included in the analysis of secondary outcomes (b, c, and d), as the linear mixed model includes all available information, also from dropouts.

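### The t-test that leads the analysis of bolus counts (secondary outcome d) is covered only by a missing-data rule that is valid for a mixed model

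*SAP*

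**What the plan says.** SAP 4.6.1.2 gives two analyses of the bolus count. The first is the t-test: "Number of bolus doses after the first 24- and 48 hours will be compared between the treatment arms by an independent samples t-test". The second is a model: "In addition, linear mixed model with the same random and fixed effects as for outcome c will be estimated". The model for outcome c is described in 4.6.1.1: "Linear mixed model with random effects for patients and slopes will be estimated".

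Section 4.6.3 ranks the methods: "Independent samples t-test for outcomes d) and f). In addition, linear mixed model for outcome c) and f". The t-test therefore leads for d, and the mixed model planned for d in 4.6.1.2 is not listed.

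Section 4.6.6 includes all patients with at least one measurement in the analysis of "secondary outcomes (b, c, and d), as the linear mixed model includes all available information, also from dropouts". For the t-test on the primary outcome, 4.4.2 has a rule of its own: "Patients will be excluded from analyses of primary outcome if data on the outcome variable is missing". Nothing comparable is written for the t-test on d.

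The outcome letters shift. The bolus count is d in 4.3 but b among the research questions in 1.3.1.2 ("Is there a difference in number of bolus doses after 24 and 48 hours between the groups") and the null hypotheses in 2.4.1.1 ("There is no difference in number of bolus doses from PCA in the SC and IV group"). Since 4.6.6 names both b and d, bolus counts are covered under either lettering.

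**The concern.** A mixed model on repeated 12 h counts can use the intervals a patient completed before leaving. A t-test needs one number per patient, and a patient who leaves at 20 h has no 48 h total. The ground given in 4.6.6 therefore does not carry over to the test that 4.6.3 puts first.

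Two ways of running the t-test remain, and neither is satisfactory:

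- **Partial counts.** Following the inclusion rule in 4.6.6, whatever was counted before exit stands in for the 24 h or 48 h total. The arm losing more patients then seems to need fewer boluses.
- **Completers.** Leavers are omitted. This contradicts 4.6.6, costs sample size, and is biased if patients with high or low bolus need leave more often.

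The SAP expects 25% dropout (4.9), so the choice may decide the data of several patients per arm in a named hypothesis test.

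**Working it through.** **Figures in the SAP.** The SAP gives no figure for outcome d. Its sample size for the primary outcome (difference 12 h, SD 12 h, 5% two-sided, 90% power) reproduces: the exact t-test calculation gives 22.02, hence 23 per arm. Dropout inflation gives 23/0.75 = 30.7, against the stated 30. At 25% dropout, 30 × 0.25 = 7.5 patients per arm could lack a full 48 h count. This is an upper bound, because 4.9 does not say how much dropout falls inside the 48 h.

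**Assumptions, none in the SAP.** 8 boluses per 48 h in one arm and 60% more (12.8) in the other; gamma-Poisson counts with shape 2; all dropout inside 48 h, with exit times uniform. The 30 per arm is from 4.9.

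**Closed-form check of the two t-test readings.** Let m be the mean, d the dropout proportion and f the fraction of 48 h observed. Then E[f] = 1 − d/2, E[f²] = 1 − d + d/3, and the variance of the count is m·E[f] + 1.5·m²·E[f²] − (m·E[f])². Power is approximately Φ(difference/SE − t critical value).

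| 48 h analysis | Difference | Variances | SE | Ratio | Approx. power | Simulated |
|---|---|---|---|---|---|---|
| No dropout, 30 per arm | 4.8 | 40.0, 94.7 | 2.12 | 2.27 | 60% | 62% |
| 25/25, partial counts | 4.8 × 0.875 = 4.2 | 38.0, 90.6 | 2.07 | 2.03 | 51% | about 52% |
| 25/25, completers, 22.5 per arm | 4.8 | 40.0, 94.7 | 2.45 | 1.96 | 48% | 48–50% |

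**Equal use (8 in both arms), partial counts, type I error.**

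- 25/25: no bias; simulated 4.5–5.2%.
- 15/35: means 7.4 and 6.6, bias 0.8, SE 1.59; about 7% by formula, about 8% simulated.
- 10/40: means 7.6 and 6.4, bias 1.2, SE 1.58; about 11% by formula, about 12% simulated.

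Completers stay at 4.6–5.1% if exit is unrelated to use. If exit depends on the 0–12 h count, they reach 5–13% (15/35) and 6–22% (10/40).

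**Mixed model on complete 12 h intervals, simulated.**

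- Unstructured covariance, 25/25, 48 h power: 56.2%, against 51.3% (partial counts) and 47.9% (completers) in the same data. Gains: 4.9 and 8.3 points. A separate run gave 58, 53 and 50%.
- Random intercept and slope, over 4–16 boluses and shape 1–4: gains of 3.5–7.5 points over partial counts and 6.7–10.1 over completers.
- At 24 h: 51–53%, against 52% and 50%, so little gain.
- Equal use, count-driven exit at 10/40, type I error: 5% unstructured, 11% partial counts, 19% completers.
- Declining use: the planned random intercept and slope model keeps 5–6% at 48 h but rises to 7–12% at 24 h. The unstructured model held 4.3–5.1% with declining use plus dropout.

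**One result that seems to disagree.** A simulation that removed a fixed number of the highest-ranking users from each arm gave 7.7–8.4% even at 25/25. That comes from trimming by rank within an arm, which makes the t-test's standard error too small. With patients leaving independently by the same rule in both arms, the level stays near 5%.

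**The case against.** The best case for the plan is that 4.6.6 has a natural object: 4.6.1.2 does plan a mixed model for d, and the rule is sound for it. On that view the t-test simply omits patients without a full count, as 4.4.2 does for the primary outcome, and 3.5 already foresees supplementary analyses of 48 h completers. Section 4.6.4 also promises differences at each time point with confidence intervals. One sentence defining the t-test's patients would then suffice.

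Part of this stands. A reader might infer that the SAP instructs analysts to enter partial counts as full totals. It does not say so; that is only one reading. A reader might also infer that false positives are likely. They are not under equal dropout with independent exits, and in a double-blind, double-dummy trial large dropout differences between arms are not the obvious expectation. If much of the 25% falls after 48 h, the effect shrinks: with 10% leaving per arm, power is 57.8% (partial counts) against 56.9% (completers). The shifting letters do not change the coverage of d, and whether counts are per interval or cumulative matters little at 48 h (58.5 against 57.6%).

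What does not stand is that the gap closes itself. Section 4.6.3 puts the t-test first and leaves the mixed model for d off its list, while 4.6.6 says that leavers are included. A sentence excluding them would remove the contradiction but keep the weaker method, with its bias when exit depends on bolus need.

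**Conclusion.** The point holds in this limited form: the leading test for d and its missing-data rule do not fit together, and 4.6.1.2 and 4.6.3 disagree on whether d has a mixed model. Both ways of running the t-test do worse at 48 h than the kind of model already planned, by about 5 points of power (partial counts) and 8 (completers). At 24 h the gain is 0–3 points.

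With equal use, type I error exceeds 5% only if dropout differs between arms (partial counts), or differs and also depends on bolus use (completers). These sizes rest on an assumed bolus rate, spread, rate ratio and exit pattern, and on all dropout falling within 48 h.

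It would be wrong to read this as a threat to the trial's main result. Outcome d is secondary, and the decision rule in 2.4.3 rests on the primary outcome alone. Priority is minor to moderate.

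**What to change.** 1. Make the mixed model planned in 4.6.1.2 the main inference for d. Fit it to counts per fully observed 12 h interval, with group, period and their interaction, and an unstructured covariance over the four intervals (REML, small-sample degrees of freedom). Report the group difference summed over 0–24 h and over 0–48 h, with 95% CIs. The unstructured covariance replaces the random intercept and slope taken from outcome c, because use and its variance may fall during titration.
2. Keep the t-test as supportive, labelled as restricted to patients observed for the full 24 h or 48 h, with a note that it is biased if exit depends on bolus need.
3. List d under the mixed model in 4.6.3, limit 4.6.6 to mixed-model analyses, and correct its outcome letters.

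The cost is SAP wording. Exact bolus times (2.5), 12-hourly assessment (4.3) and discontinuation times (3.3) are already planned. With complete data the unstructured model equals the pooled t-test on summed counts. The downsides are reliance on missing at random given earlier counts, a less direct result than a difference in totals, and no contribution from patients leaving before 12 h: about 30 × 0.25 × 12/48 = 1.9 per arm if 25% leave uniformly over 48 h.
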